- kk. PBMC samples will be collected at selected sites only. Additional PBMC samples may be taken in case of ALT flares, upon discussion with the sponsor, and may require an unscheduled visit.
- II. These samples are optional and will only be collected from participants who consent separately to this component of the study. The pharmacogenomic (DNA) sample should preferably be collected at baseline.
- mm. Adverse events and concomitant medications will be monitored from the time a signed and dated ISA ICF is obtained until completion of the participant's last ISA related procedure.
- nn. Exclusion criterion A25 regarding contraindications to the use of PegIFN α2a needs to be checked again at the end of the induction phase prior to the first dose of PegIFN α2a. If a participant's clinical status changes (including any available laboratory results or receipt of additional medical records) after screening but before the first dose of PegIFN α2a is given such that he or she meets exclusion criterion A25, then the participant should continue their study intervention until completion of the consolidation phase without the addition of PegIFN α2a.
- oo. The liver ultrasound does not need to be repeated at baseline if it was done at screening or within 6 months prior to screening.

- pp. As of Protocol Amendment 6, new participants will enroll without randomization to receive JNJ 3989+NA for 36 weeks (induction phase) and will then enter the 12 week consolidation phase during which they will have PegIFN  $\alpha$ 2a added to their treatment regimen.
- qq. Includes close monitoring for neuropsychiatric adverse events during the PegIFN α2a treatment period. Participants who develop a neuropsychiatric adverse event during PegIFN α2a treatment, will be monitored closely until the neuropsychiatric adverse event resolves, with frequent (at least weekly) follow up phone calls.
- rr. Most participants enrolled before Protocol Amendment 6 was in effect, have received JNJ 6379 as part of their study intervention. Dispensation of JNJ 6379 stopped immediately with the removal of JNJ 6379 as study intervention through an urgent safety measure. Participants have to return JNJ 6379 tablets to the site at the next scheduled visit.

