- a. All follow up study visits are to be scheduled relative to the last dose of JNJ 3989/PegIFN α2a. An unscheduled visit can be performed upon the investigator's discretion, in case of HBV DNA elevations, ALT elevations, other signs of worsening of liver disease, or for any other reason during follow up.
- Participants who withdraw consent during follow up will be offered an optional safety follow up visit.
- c. Participants who discontinue study intervention early will have an early WD visit and will enter follow up unless they withdraw consent. Participants who withdraw consent during study intervention will be offered an optional safety follow up visit to occur on the day of consent withdrawal. For the optional safety follow up visit, assessments are at the investigator's discretion and could be similar to the early WD visit.
- d. Follow up Week 8, 16, 20, 28, 32, 40, and 44 visits are not required for participants who did not complete NA treatment at Follow up Week 2 and for participants who have restarted NA treatment during the follow up period, provided that their HBV DNA and ALT values are stable.
- e. In between study visits, participants will take NA orally at home and will bring their NA with them to each study visit. At study visits, NA should be taken on site. PegIFN α2a should be administered weekly, preferably in the evening by self injection. If desired, participants can also choose to have the weekly administration of PegIFN α2a performed on site irrespective of the time of day. PegIFN α2a should preferably be administered in the evening prior to the sparse PK visit, or alternatively in the morning of the visit on site.

- f. No JNJ 3989/PegIFN α2a will be administered or dispensed during follow up. Administration/Dispensation of NA is only applicable for participants who could not stop NA treatment, or for those who met the NA re treatment criteria. In between study visits, participants will take NA at home and they will bring their NA treatment with them to each study visits, the NA treatment should be taken on site.
- g. If the NA treatment completion criteria are met at consolidation Week 12, treatment with NA will be completed at FU Week 2.
- h. Complete physical examination, including body weight, skin examination, and other body systems.
- i. Vital signs include supine SBP, DBP, pulse rate, and body temperature.

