	Cohort 2: Participants receive PegIFN- <math>\alpha</math>2a: Date of first PegIFN- $\alpha$ 2a intake  Participants who did not receive PegIFN- <math>\alpha</math>2a: Date of any study agent intake after Week 36 visit date  Otherwise: Missing	Cohort 2: Participants who did not withdraw from the study prior to the Consolidation Week 12 visit date: Min{Max[last intake date of any study agent (excluding NA), CW12], JNJ-3989 discontinuation date a } + 5 days a or cut-off date b , whichever occurs first  Participants who withdrew from the study prior to the Consolidation Week 12 visit date: Min[JNJ-3989 discontinuation date a , early study withdrawal visit date] + 5 days a or cut-off date b , whichever occurs first  Otherwise: Missing
Follow-up	Participants who did not withdraw informed consent during induction or consolidation phase: Max[End date of induction phase, End date of consolidation phase] +1  Otherwise: Missing	Max[study discontinuation date, study completion date] or cut-off date b , whichever occurs first  Otherwise: Missing

a Addition of 5 days is only applicable for JNJ-3989 discontinuation due to Adverse Events and Concomitant Medications.

b Cut-off dates will be defined to match the prespecified timepoints for DRC safety monitoring, interim analyses and the primary and final analyses, respectively.

c CW = Consolidation Week

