### 2.1.2.3. Follow Up Relative Day

Follow Up (FU) start date (FU Day 1) is defined in [Table 1](#). All efficacy and safety assessments during the FU phase will be assigned a day relative to this date. The FU study day in the FU treatment phase (ADY) is defined as:

$$\text{FU ADY} = \text{visit date} - \text{FU start date} + 1$$

for visits on or after FU Day 1.

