## Consolidation Phase

- For JNJ-3989: (Total number of injections received/ 3) \* 100%
- For PegIFN- $\alpha$ 2a: (Total number of injections received/ 12) \* 100%

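### One protocol footnote dates follow-up visits from the last JNJ-3989/PegIFN dose but the SAP counts them from about consolidation Week 12, so by-visit labels can slip, most easily at FU Week 4

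*Protocol*

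**What the plan says.** **Site clock.** Protocol Section 1.3.2, footnote a: "All follow up study visits are to be scheduled relative to the last dose of JNJ 3989/PegIFN α2a".

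**Analysis clock.** SAP Section 2.1.2.3 sets a follow-up start date and states: "All efficacy and safety assessments during the FU phase will be assigned a day relative to this date". Table 1 gives that start as "Max[End date of induction phase, End date of consolidation phase] +1". For participants not withdrawn before CW12, consolidation ends on "Min{Max[last intake date of any study agent (excluding NA), CW12], JNJ-3989 discontinuation date". A Table 1 footnote limits the extra five days: "Addition of 5 days is only applicable for JNJ-3989 discontinuation due to Adverse Events and Concomitant Medications".

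**Doses in consolidation.** SAP Section 4.7 takes PegIFN compliance as "Total number of injections received/ 12" and JNJ-3989 compliance out of three injections. The schedule places those three on consolidation (C) Day 1, C Week 4 and C Week 8.

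**Participants without PegIFN.** Protocol Section 1.3.1, footnote nn: if a PegIFN contraindication appears before the first dose, "then the participant should continue their study intervention until completion of the consolidation phase without the addition of PegIFN α2a". Protocol Section 4.1 likewise keeps JNJ-3989 and NA going when PegIFN stops early.

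**Protocol text pointing to CW12.** Section 1.3.2 heads the C Week 12 column as end of study intervention (EOSI), and Appendix 1 defines EOSI as the time of the last administration. Section 6.6.1 has JNJ-3989 and PegIFN completed at Consolidation Week 12. The synopsis gives a total participation of 100 to 102 weeks.

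**The concern.** The two documents can start the follow-up clock on different dates, and the protocol does not settle the matter within itself. SAP Section 2.1.3 assigns every result to a time point by its follow-up day, and keeps only the result nearest the target day when two share a window. An anchor difference of a week or more can therefore relabel a visit or remove a value from by-visit tables.

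FU Week 4 is the weak spot because the early windows are narrow relative to the offset. The schedule draws anti-HBs at FU Week 4 and not at FU Week 2, and the only follow-up ECG is at FU Week 4. SAP Section 5.4.2.2.2 names FU Week 4 for an anti-HBs summary. The first PegIFN-responder subgroup (SAP Section 2.5.1) and the correlations in SAP Section 5.4.1.3.1 use intervals that end at FU Week 4.

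**Working it through.** **Check on a stated figure.** Screening 4 to 6 + induction 36 + consolidation 12 + follow-up 48 = 100 to 102 weeks, as the protocol states. This works only if follow-up runs from CW12. Counted from a last PegIFN dose one week earlier, it would be 99 to 101.

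**Inputs**
- Protocol follow-up study days *d*: FU Week 2 = 15, Week 4 = 29, Week 8 = 57, Week 12 = 85, Week 24 = 169, Week 28 = 197, Week 36 = 253, Week 48 = 337, each ±4 days. CW12 is C Day 85 ±3 days.
- SAP Table 2c windows: Week 2 [1, 22], Week 4 [23, 43], Week 8 [44, 71], Week 20 [128, 155], Week 24 [156, 183], Week 32 [212, 239], Week 44 [296, 323], Week 48 from 324.
- Last-dose day *L*: 12 weekly PegIFN doses from C Day 1 end on 1 + 11 × 7 = C Day 78. Missing only the twelfth gives C Day 71. With no PegIFN after C Week 8, the last dose is JNJ-3989 on C Day 57.

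**Formula.** Taking the last dose as follow-up Day 1, the visit falls on C Day *L* + *d* − 1. With CW12 on C Day 85 and JNJ-3989 not discontinued, follow-up starts on C Day 86. So SAP follow-up day = (*L* + *d* − 1) − 86 + 1 = *L* + *d* − 86.

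| Visit held | L = 78 | L = 71 | L = 57 |
|---|---|---|---|
| FU Week 2 | day 7, Week 2 | C Day 85 (the CW12 day) | C Day 71, before CW12 |
| FU Week 4 | day 21, **Week 2** | day 14, **Week 2** | C Day 85 (the CW12 day) |
| FU Week 8 | day 49, Week 8 | day 42, **Week 4** | day 28, **Week 4** |
| FU Week 12 | day 77, Week 12 | day 70, **Week 8** | day 56, **Week 8** |
| FU Week 24 | day 161, Week 24 | day 154, **Week 20** | day 140, **Week 20** |
| FU Week 36 | day 245, Week 36 | day 238, **Week 32** | day 224, **Week 32** |
| FU Week 48 | day 329, Week 48 | day 322, **Week 44** | day 308, **Week 44** |

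**Which value is kept (L = 78).** Distances from target day 15 are |21 − 15| = 6 and |7 − 15| = 8. The FU Week 4 result is kept as FU Week 2, and the FU Week 4 window is empty. For tests drawn only at FU Week 4, nothing is displaced but the label is wrong.

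**Sensitivity (L = 78)**
- Last dose counted as Day 0: FU Week 4 is day 22, still FU Week 2.
- Five days added to the end of consolidation: 21 − 5 = day 16, still FU Week 2.
- Last dose two days later, on C Day 80: 80 + 29 − 86 = day 23, correctly filed.
- All 7 × 9 = 63 combinations of CW12 ±3 and FU ±4 days: FU Week 4 is misfiled in 42 (35 with the Day 0 count); FU Week 24 in 3.

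**Discontinuation date.** If a completer's JNJ-3989 discontinuation date were recorded as the last injection (C Day 57), the outer minimum would start follow-up on C Day 58. The CW12 visit itself would then be day 85 − 58 + 1 = 28, filed as FU Week 4.

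**With one anchor.** Scheduled from CW12 (*L* = 85), FU Weeks 4, 24 and 48 fall on days 28, 168 and 336, and all 13 follow-up visits land in their own windows.

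**The case against.** The strongest reply is that a single footnote stands against the rest of the protocol. The EOSI column heading and definition, Section 6.6.1 and the 100 to 102 weeks all point to CW12, which agrees with the SAP. Sites that use CW12 see no mismatch. This stands: a reader might infer that sites do schedule from the last dose, but the documents do not show it. They show only that the footnote tells them to.

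A reader might also infer that all, or two-thirds, of FU Week 4 results are misfiled. Neither is established. The nominal result turns on one day, and 42 of 63 treats all permitted offsets as equally likely and fixes the last dose at C Day 78. Section 6.5 allows a two-day PegIFN delay around COVID-19 vaccination, and that alone can restore the correct label.

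A third tempting inference is damage to the primary endpoint. For full-PegIFN completers FU Week 24 stays in its window. Participants who continue NA cannot be responders wherever the visit is filed. Those off NA attend every four weeks, so for *L* = 57 their FU Week 28 visit (day 57 + 197 − 86 = 168) fills the FU Week 24 window. The ±12-week rule (Protocol Section 9.4.1.1, SAP Section 5.2.2.1.3) is a further safeguard, and SAP Amendment 4 reports only one participant who met the NA completion criteria and stopped NA.

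Nor are results lost outright. Listings and spaghetti plots keep every measurement, and the last visit also appears under the end-of-study label.

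For *L* = 57 the literal schedule cannot be run in the stated order, because FU Week 2 precedes the CW12 visit whose results decide NA completion. That makes widespread shifting hypothetical in this group, but it is itself a contradiction in the documents. The number of such participants is not given.

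**Conclusion.** The concern holds as an inconsistency of moderate severity. Followed as written, the footnote and SAP Table 1 differ by one week for a full PegIFN course (C Day 78 against 85), which is enough to move an on-schedule FU Week 4 visit into FU Week 2. A last dose on C Day 71 or earlier files FU Week 8 and all later visits one window early. For NA-continuers, who may skip the intermediate visits, this can empty the FU Week 12, 24, 36 and 48 windows although each visit was made.

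The exposed results are by-visit marker, anti-HBs and ECG summaries, and intervals ending at FU Week 4. If those intervals are built from labelled visits, a full-PegIFN completer loses the FU Week 2 value, and a participant with an earlier last dose contributes the FU Week 8 visit. In a descriptive study without a formal hypothesis these tables matter, but the effect on the primary endpoint is small.

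This rests on sites reading footnote a literally, first PegIFN on C Day 1, CW12 on C Day 85, and no earlier JNJ-3989 discontinuation date. The SAP does not always start follow-up at or after CW12; a reader of the inner maximum alone might think so, but the outer minimum overrides it.

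**What to change.** 1. **Protocol.** Reconcile footnote a with the EOSI column and definition, Section 6.6.1 and the stated duration. For participants who reach CW12, follow-up visits would be counted from the CW12/EOSI visit, as in SAP Table 1; only for those who discontinue JNJ-3989 before CW12 would they be counted from the last dose. The order of CW12, FU Week 2 and the NA-completion decision when the last dose is early must be reconciled by the sponsor.
2. **Visits already made.** Check from recorded dose and visit dates which anchor each site used. Compute the Table 2c follow-up day from that anchor, keeping the CW12 visit in the consolidation phase. Simply redefining Day 1 as the last dose for everyone would create a new error: with a last dose on C Day 57, the CW12 visit becomes follow-up day 85 − 57 + 1 = 29 and is labelled FU Week 4.
3. **SAP Table 1.** State which date counts as the JNJ-3989 discontinuation date for participants who complete treatment.

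The cost is one footnote, a short addition to Table 1 and Section 2.1.2.3, and a date check on existing data. No new visits or samples are needed.

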Study Phase	Open-label Consolidation Phase						Follow-up a,b													
Consolidation (C)/ Follow up (FU) Week (W)	C W2	C W4	C W6	C W8	C W12 / EOSI / WD°	FU W2	FU W4	FU W8 d	FU W12	FU W16 d	FU W20 d	FU W24	FU W28 d	FU W32 d	FU W36	FU W40 d	FU W44 d	FU W48 / EOS		
C / FU Study Day (Window)	15 +/ 3d	29 +/ 3d	43 +/ 3d	57 +/ 3d	85 +/ 3d	15 +/ 4d	29 +/ 4d	57 +/ 4d	85 +/ 4d	113 +/ 4d	141 +/ 4d	169 +/ 4d	197 +/ 4d	225 +/ 4d	253 +/ 4d	281 +/ 4d	309 +/ 4d	337 +/ 4d		
Urinalysis r		X		X	X	X t	(X)	(X)	(X)	(X)	(X)	(X)	(X)	(X)	(X)	(X)	(X)	X		
Urine chemistry s		X		X	X	X t	(X)	(X)	(X)	(X)	(X)	(X)	(X)	(X)	(X)	(X)	(X)	X		
Urine pregnancy test (women of childbearing potential only)		X		X	X		X v	X	X v	X v	X v	X v	X v	X v	X v	X v	X v	х		
AFP test p,u					X							X						X		
TSH and T4					X															
Efficacy Evaluations																				
Fibroscan w					(X)							(X)						(X)		
HBV Virology																				
Blood sampling for HBV DNAkk	X	X	X	X	X	X	X	X	X	X	X	X	X	X	X	X	X	X		
Blood sampling for HBV RNA x		X		X	X	X	X	X	X	X	X	X	X	X	X	X	X	X		
Sampling for viral genome sequencing y		X			X		X		X		X		X	X		X		X		
HBV Serology																				
Blood sampling for:																				
Anti HBs and anti HBe					X		X		X			X			X			X		
HBsAg and HBeAg (qualitative)					X				X			X						X		
HBsAg (quantitative)	X	X	X	X	X	X	X	X	X	X	X	X	X	X	X	X	X	X		
HBeAg (quantitative)	X	X	X	X	X	X	X	X	X	X	X	X	X	X	X	X	X	X		
HBcrAg x		X			X		X		X			X			X			X		
Exploratory serology 		X			X	X	X	X	X	X	X	X			X			X		
Clinical Pharmacology Assessments																				
Blood sampling for sparse PK of JNJ 3989, PegIFN α2a and NA aa		Xbb		X bb,e e	(X)cc															
Blood sampling for intensive PK of JNJ 3989, PegIFN α2a and NA (PK substudy) dd				X																
Exploratory Host Biomarkers																				
Whole blood RNA gene expression		X			X							X						X		
Whole blood single cell profiling		X			X	X	X	X	X	X		X			X			X		
Host serum proteins (eg, cytokines)		X			X		X	X	X	X		X			X			X		
Antidrug antibodies (to JNJ 3989 and PegIFN α2a)		X		X	X		X		X			X						X		

CONFIDENTIAL – FOIA Exemptions Apply in U.S. Status: Approved, Date: 25 November 2021

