- r. Urinalysis by dipstick: specific gravity, pH, glucose, protein, blood, ketones, bilirubin, urobilinogen, nitrite, leukocyte esterase, and microscopic analysis if needed. The dipstick reading should be done as soon as possible and in accordance with the manufacturer's recommendation. In case of a positive dipstick result, a urine sample will be set aside for additional examination of the positive parameter at the central laboratory (eg, quantification as applicable).
- s. Urine chemistry sample (quantitative measurement); creatinine, sodium, phosphate, glucose, protein, and albumin.
- t. A urinalysis and urine chemistry sample will be taken at FU Week 2. In case of abnormalities, the tests should be repeated at the following visits until resolution.
- u. Additional samples may be collected for AFP testing in case of ALT flares.
- v. Urine pregnancy tests will be provided to the participants for at home use as necessary to ensure urine pregnancy tests are performed at least every 4 weeks. Results will be reported at the next visit. If a urine pregnancy test is positive, the investigator needs to be informed immediately by the participant.
- w. Only applicable to participants who are enrolled at a site with an on site Fibroscan device.
- x. HBcrAg and HBV RNA samples may be batched and only selected samples may be tested at the sponsor's request. Samples can be used for assessment of other serologic/virologic markers of HBV.
- y. Samples may be sequenced based on the sponsor virologist's request, considering the HBV DNA levels. A sample for viral genome sequencing will be taken at an unscheduled visit for confirmation of virologic flare. In case of a virologic flare, additional samples for viral sequencing may be taken.
- z. Exploratory serology samples may be analyzed at the sponsor's discretion. Samples may be used to assess virologic or serologic markers of HBV.
- aa. All participants will have sparse PK sampling for JNJ 3989, NA, and PegIFN α2a. Bioanalysis of NA and PegIFN α2a is optional at the discretion of the sponsor. Bioanalysis of JNJ 6379 may also be done on samples collected from participants who received JNJ 6379 up to Protocol Amendment 5.

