#### 6.2.3.1.1. Proximal Renal Tubular Function Proteinuria by Quantitative Assessment

Total urine protein, total urine albumin, UPCR and UACR will be summarized by cohort and visit using descriptive statistics.

The number and proportion of participants with UACR and UPCR results in the following categories over time will be tabulated:

- UACR:  $< 30$ ,  $\geq 30$  to  $300$ ,  $>300$  mg/g
- UPCR:  $< 200$  mg/g versus  $\geq 200$  mg/g

Median (Q1, Q3) percent change from baseline over time will be plotted by cohort. The evolution over time of total urine protein and total urine albumin will also be presented.

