### **6.2.3.1.2. Proteinuria by Urinalysis (Dipstick)**

Treatment-emergent proteinuria by urinalysis (dipstick) over time will be summarized by cohort. Cross-tabulation of grades overtime versus baseline will also be presented.

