### **6.2.3.1.4. Phosphate Excretion**

Other renal biomarkers include FEPO4 that will be summarized by cohort and visit using descriptive statistics.

FEPO4 will be calculated as follows:

- Based on unadjusted serum creatinine:

$$\text{FEPO4 (\%)} = (\text{SCr} \times \text{UPO4}) / (\text{SPO4} \times \text{Ucr}) \times 100 \text{ (\%)}$$

Where SCr is serum creatinine concentration, UPO4 is urine phosphate concentration, SPO4 is serum phosphate concentration, and Ucr is urine creatinine concentration.

The proportions of participants with FEPO4  $\leq 10\%$  and  $> 10\%$  will be tabulated.

The baseline, post-baseline, and change from baseline in FEPO4 will be summarized by cohort and visit using descriptive statistics. Median (Q1, Q3) change from baseline in FEPO4 over time will be plotted by cohort.

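### Urine tests at FU Weeks 4 to 44 are repeated only after an abnormal result, but the SAP summarises urine renal markers by visit as if everyone were sampled

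*Protocol*

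**What the plan says.** **Sampling.** In Protocol 1.3.2 (Schedule of Activities), the urinalysis and urine chemistry rows carry an unconditional mark at FU Week 2 (with footnote t) and at FU Week 48. Every visit from FU Week 4 to FU Week 44 has a bracketed mark. Footnote t requires a sample at FU Week 2 and adds: "In case of abnormalities, the tests should be repeated at the following visits until resolution". The bracketed marks have no footnote of their own, so tying them to footnote t is an inference, but it is the natural reading.

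**What is measured.** Urine chemistry covers "creatinine, sodium, phosphate, glucose, protein, and albumin". It therefore supplies the urine part of UPCR, UACR and FEPO4. The dipstick covers "specific gravity, pH, glucose, protein, blood, ketones, bilirubin, urobilinogen, nitrite, leukocyte esterase, and microscopic analysis if needed".

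**Planned displays.**
- SAP 6.2.3.1.1: "Total urine protein, total urine albumin, UPCR and UACR will be summarized by cohort and visit using descriptive statistics". It also calls for UACR and UPCR category proportions over time, a plot of median (Q1, Q3) percent change from baseline, and a display of urine protein and albumin over time.
- SAP 6.2.3.1.2: "Treatment-emergent proteinuria by urinalysis (dipstick) over time will be summarized by cohort". A cross-tabulation against baseline is added; no plot is specified.
- SAP 6.2.3.1.4: FEPO4 by cohort and visit, and "Median (Q1, Q3) change from baseline in FEPO4 over time will be plotted by cohort".

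SAP Table 2c makes all 13 follow-up visits analysis time points. None of the three sections excludes a visit, defines a denominator or mentions conditional sampling.

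**The concern.** A by-visit median or percentage describes whoever was sampled. At FU Weeks 2 and 48 that is the cohort; in between it is people selected for an earlier urine abnormality. A table or line joining these visits compares different groups, and a reader would take the difference for a change over time.

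The safety question is a live one. Renal complications are an adverse event of special interest (Protocol 8.3.6, SAP 6.1.3). Protocol 2.3.2.2.2 suspects that JNJ-6379 combined with TDF contributes to tubular toxicity. Retinol binding protein and beta-2-microglobulin are not scheduled after Consolidation Week 12, so the urine tests are the main tubular evidence in follow-up. The same SAP handles uneven data elsewhere: it limits seroconversion to visits with antibody results (5.3.1.1.5), restricts the denominator for off-treatment seroclearance (5.3.2.1.2), and requires at least 5 participants for a sequencing output (7.5). The renal sections have no such rule.

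**Working it through.** Neither document gives an expected number of retests, so there is no plan figure to reproduce. I counted the affected visits, then checked direction by simulation.

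**1. Conditional visits.** 13 follow-up visits − 2 fully sampled (FU Weeks 2 and 48) = 11.

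**2. Which of the 11 matter.**
- FEPO4 = (SCr × UPO4) / (SPO4 × UCr) × 100 needs serum creatinine and serum phosphate. At FU Weeks 8, 16, 20, 28 and 32 blood chemistry is limited to liver function tests (footnote q). So 11 − 5 = 6 visits remain: FU Weeks 4, 12, 24, 36, 40 and 44.
- Participants who stay on NA or restart it, with stable HBV DNA and ALT, need not attend FU Weeks 8, 16, 20, 28, 32, 40 and 44 (footnote d). That leaves 11 − 7 = 4: FU Weeks 4, 12, 24 and 36. The SAP Amendment 4 history records one participant who stopped NA, so this is the usual case.

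**3. Direction.** Model: log UPCR = person effect + visit noise, with an optional lasting personal shift after baseline of mean 0, so the cohort does not change. All parameters are assumptions: median 80 mg/g; person SD 0.5 and noise SD 0.5 on the log scale (scenario E: 0 and 0.7). Everyone is tested at FU Week 2; later tests occur only while the previous value exceeds 200 mg/g, the SAP's UPCR cut-point. There were 400,000 simulated people, with counts scaled to the 33 planned for Cohort 2. Results at FU Week 4:

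| Scenario | n tested | Median among tested, mg/g (all: 80) | Share ≥200 mg/g, tested vs all | Median change from baseline, tested |
|---|---|---|---|---|
| A. Stable persons, independent noise | 3.2 | 149 | 32.3% vs 9.7% | +0.7% |
| B. A plus lasting personal shifts (SD 0.4) | 4.3 | 182 | 44.4% vs 13.0% | +37.4% |
| C. A with noise autocorrelation 0.5 in follow-up | 3.2 | 202 | 50.9% vs 9.7% | +36.9% |
| D. B plus 30% retested for an unrelated lasting abnormality | 12.9 | 98 | 20.1% vs 12.9% | +8.0% |
| E. Noise only, no person effect | 3.2 | 80 | 9.6% vs 9.5% | −0.1% |

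At FU Week 48, where all are sampled, the median is 80 mg/g in every scenario and the median change is within 0.4 percentage points of zero.

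**4. Why change from baseline can stay flat.** In A, the baseline and FU Week 4 values are each the person effect plus independent noise. Given FU Week 2 they have the same distribution, so their difference centres on zero. Levels still rise, because people with high person effects are selected.

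**5. The denominator.** A tested-only denominator gives the tested shares in the table. If all in follow-up are the denominator, untested people count as below the threshold:
- A: 9.7% × 32.3% = 3.1%, against a true 9.7%.
- B: 13.0% × 44.4% = 5.8%, against 13.0%.
- D: (12.9 / 33) × 20.1% = 7.9%, against 12.9%.

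So in A, B and D one denominator overstates and the other understates; neither recovers the cohort value.

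**The case against.** The best defence is that the distortion is limited and partly visible. Any urine abnormality triggers a repeat, so someone retested for leukocyte esterase is not selected on protein or phosphate; scenario D shows how this dilutes the effect. The normal value that ends a series stays in the data. The median (Q1, Q3) plots show change from baseline, which selection on level need not move. General laboratory tables report n at each time point (SAP 6.2.2), spaghetti plots are already planned (6.2.3.1), worst-grade analyses are per participant and phase, and FU Week 48 is fully sampled. JNJ-6379 stopped at Amendment 6 and was not given to Cohort 2, so follow-up is not in general its washout period. All safety analysis is descriptive.

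These points stand, and they limit the claim. They do not remove it. Printing n shows that few were tested, not that they were chosen for being abnormal. A median from about 3 selected people beside medians from about 33 is not a visit effect, whatever n is shown.

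**Conclusion.** The mismatch is real: sampling at FU Weeks 4 to 44 depends on an earlier urine abnormality, and the SAP summarises those visits as if sampling were complete. Levels, and percentages based on those tested, will tend to look worse there when the marker persists within a person and is related to the trigger. Median change from baseline shifts only if post-baseline deviations also persist. The size cannot be stated: it depends on how many are retested and for which abnormality, and the simulated figures rest on assumed parameters.

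A reader might infer that renal markers must appear to worsen in follow-up by construction. The documents do not support that:
- The trigger is broader than protein or phosphate, and scenario E shows no distortion.
- The specified median plots are of change from baseline, and dipstick proteinuria is not plotted.
- FEPO4 is affected at no more than 6 visits, and for most participants the conditional visits are mainly FU Weeks 4, 12, 24 and 36.
- eGFR comes from blood tests that do not depend on a urine result.

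The issue touches descriptive safety displays only, not the primary endpoint. It still merits correction, because the outputs as written would mislead on an event of special interest and the remedy is cheap.

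**What to change.** In SAP 6.2.3.1.1, 6.2.3.1.2 and 6.2.3.1.4:
- Limit follow-up by-visit statistics, category percentages and median plots of urine markers to FU Week 2 and FU Week 48.
- Show FU Week 4 to 44 results only in listings or individual profiles, with the number tested out of the number in follow-up and the number resolved out of the number abnormal at FU Week 2.
- State the denominator for every proportion.

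The cost is SAP wording and output shells, with no extra samples and no protocol change. The downside is that there is no cohort-level urine summary at the intermediate visits.
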